#### 9. CHANGES FROM METHODS PLANNED IN THE PROTOCOL

The statement of the primary estimand given in Section 6.2.1.2 clarified that the target population excludes e4/e4 participants, that the primary estimand specified in the latest version of the protocol did not specify this exclusion. This clarification does not result in any differences for summaries or analyses.

The criteria for PPS in Section 5.3.2 are updated as the one specified in the protocol was too general and did not meet the needs of PPS.

The summary of physical examinations will not be performed, since clinically significant physical examination changes will be captured in the AE summaries.

The supportive analysis using LME model is removed from this SAP. The primary analysis using the pMMRM model is based on the assumption of proportionality, which is an inherit assumption of the LME model. If the assumption of proportionality is not met under the pMMRM model, the results of analysis using the MMRM model will be used to interpret the study. For this reason, the supportive analysis using LME model has been removed from SAP.

Safety analyses will primarily be performed for the Non-e4/e4 Set, instead of the Safety Set as specified in the protocol, because of the removal of the e4/e4 participants from the participant population being studied. The AL002-2 study originally included enrollment of participants who were APOE e4 homozygotes (e4/e4). However, further enrollment of participants with this APOE genotype was permanently stopped after the evaluation of safety among the early enrolled participants with e4/e4. Therefore, the primary objective of the study changed to the assessment of AL002 in the participants without e4/e4.

The exploratory analyses of WLSA data (optional study) and genetics will be excluded from the SAP.

# **Statistical Analysis Plan**Protocol No. AL002-2

Last Revision Date: 12 Aug 2025

# 10. STATISTICAL SOFTWARE

SAS® Version 9.4 or later in the UNIX environment will be used for all statistical analyses.

Protocol No. AL002-2 Last Revision Date: 12 Aug 2025

#### 12. APPENDIX

#### Delta method:

Let X and Y be two random variables with means  $\mu_X$  and  $\mu_Y$ , respectively; and let  $R(\mu_X, \mu_Y) = \frac{\mu_X}{\mu_Y}$  be the ratio. Then

$$\frac{\partial y}{\partial \mu_X} R (\mu_X, \mu_Y) = \frac{1}{\mu_Y}$$

$$\frac{\partial y}{\partial \mu_Y} R (\mu_X, \mu_Y) = -\frac{\mu_X}{\mu_Y^2}$$

$$E\left(\frac{X}{Y}\right) \approx \frac{\mu_X}{\mu_Y} \qquad (1)$$

$$Var\left(\frac{X}{Y}\right) \approx \frac{1}{\mu_Y^2} VarX + \frac{\mu_X^2}{\mu_Y^4} VarY - 2\frac{\mu_X}{\mu_Y^3} Cov(X, Y)$$

When *X* and *Y* are independent (e.g., in two independent treatment arms),

$$Var\left(\frac{X}{Y}\right) \approx \frac{1}{\mu_Y^2} VarX + \frac{\mu_X^2}{\mu_Y^4} VarY$$
 (2)

#### Percent slowing of decline estimation based on MMRM

When applying the Delta method to the MMRM outputs,  $\mu_X$  and  $\mu_Y$  will be substituted by the estimated LSMs of the CFB at the end-of-study visit (time = 4 in the specific example below), and their variances will be the estimated variances. The table below presents the related parameter estimates that can be used for the percent slowing of decline estimation. Substituting these related estimates into formula (1) and formula (2) will yield the percent slowing of decline estimation and the corresponding p-values.

Group	Time	Estimate	Standard Error
P	4	$\mu_Y = 4.5489$	$\sqrt{VarY} = 0.6143$
T	4	$\mu_X = 3.0991$	$\sqrt{VarX} = 0.5903$

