#### 7.4 Efficacy Analyses

The FAS will be used for all efficacy analyses, except for the analyses specified in Section 7.4.1.5, unless otherwise specified.

The primary estimand as described in Section 6.2.1.2 will be used for all efficacy analyses, except for the analyses specified in Section 7.4.1.5 which are based on the supportive estimand, and unless otherwise specified.

Missing data will be assumed missing at random (MAR) for all efficacy analyses, except for the analyses specified in Section 7.4.1.4, and unless otherwise specified. Sensitivity analysis to assess the impact of the missingness assumption will be performed using a Pattern Mixture Model (PMM) as described in Section 7.4.1.4.

For each continuous efficacy endpoint, the number of participants with efficacy outcomes, mean, SD, median, Q1, Q3, min, and max, at baseline and each scheduled post-baseline visit, along with CFB and PCFB to each scheduled post-baseline visit, will all be reported and accompany the estimates from the inferential statistical models. The same applies to subgroups specified in Section 7.4.3.

Unless otherwise indicated, all statistical tests will be 1-sided. However, 2-sided p-values will be reported for all tests. A significance level of 0.05 (1-sided) will be used for primary endpoint, with significance achieved if the 2-sided p-value is less than 0.10, and in the direction of indicating more efficacy for non-placebo than for placebo.

In the case of multiple values in an analysis visit window, data will be selected for analysis as described in Section 7.1.3.2, separately for each estimand.

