## 7.4.1.2 Supportive Analysis using Mixed-Effects Model for Repeated Measures (MMRM)

A restricted maximum likelihood based MMRM will be used as a supportive analysis to assess the primary endpoint.

The SAS® MIXED procedure will be used to fit an MMRM with CFB in CDR-SB at each scheduled post-baseline visit (Week 24, 48, 72, and 96) as the dependent variables and the fixed effects will include following items:

- Treatment group,
- Visit (categorical, as week),
- Visit-by-treatment interaction,
- Baseline CDR-SB score (covariate),
- APOE e4 status (covariate, e4 carrier vs non-e4 carrier).

An unstructured covariance matrix will be used to model within participant variance-covariance errors. If the unstructured covariance structure matrix results in a lack of convergence, the following tests will be used in sequence:

- Heterogeneous Toeplitz (TOEPH) covariance structure,
- Heterogeneous first-order autoregressive (ARH(1)) covariance structure,
- Heterogeneous compound symmetry (CSH) covariance structure,
- Toeplitz (TOEP) covariance structure,
- First-order autoregressive (AR(1)) covariance structure,
- Compound symmetry (CS) covariance structure.

In the case that a structured variance-covariance matrix is used to enable the model to converge, the "sandwich" estimator of the variance-covariance matrix will be employed by using the "empirical" option in the SAS PROC MIXED procedure.

The Kenward-Rogers approximation will be used to estimate the denominator degrees of freedom when the covariance is unstructured.

Least squares means (LSMs) and their difference between each treatment group and the placebo will be estimated for Week 24, 48, 72, 96 and "overall" (the average of Week 24, 48, 72, and 96) for each of CDR-SB. The LSMs are interpreted as the expected CFB in the primary efficacy outcome. LSMs and standard errors (SEs) will be shown for each active treatment group and placebo. In addition, the percent slowing of decline expressed as the ratio of negative difference in LSMs over the LSM of placebo (i.e., [(–difference in LSM) / (LSM of placebo)] × 100%) will be displayed for each active treatment group. And its CI will be derived using the Delta method (refer to APPENDIX for more details on the derivation).

LSMs line plots over time will be displayed for the primary endpoint with separate lines for each treatment group.

Protocol No. AL002-2 Last Revision Date: 12 Aug 2025

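### The SAP appendix labels the treatment/placebo ratio as percent slowing: its example would give 68% where Section 7.4.1.2 defines 32%, and no null is stated for the p-value

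*SAP*

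**What the plan says.** SAP Section 7.4.1.2 (supportive MMRM) asks, for each active group, for "the percent slowing of decline expressed as the ratio of negative difference in LSMs over the LSM of placebo". With T for the treatment LSM and P for the placebo LSM, that is -(T - P)/P = 1 - T/P. The section then turns to the appendix for the interval: "And its CI will be derived using the Delta method (refer to APPENDIX for more details on the derivation".

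The appendix (Section 12, Delta method) gives formula (1), the mean of X/Y as the ratio of the two means. It prints a general variance with a Cov(X,Y) term, then formula (2), which drops that term when X and Y are independent, for instance "in two independent treatment arms". Its last subsection says that the two means "will be substituted by the estimated LSMs of the CFB at the end-of-study visit". The example table labels group P as Y and group T as X, and the text says: "Substituting these related estimates into formula (1) and formula (2) will yield the percent slowing of decline estimation and the corresponding p-values". No result is printed for the example, and neither a test statistic nor a null value is given.

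**The concern.** Taken at its word, the appendix equates T/P with percent slowing. That scale runs backwards. A drug with no effect (T = P) would show 100%, a drug that halts decline would show 0%, and a weaker drug would look better than a stronger one. An interval built from formulas (1) and (2) would be centred on the wrong quantity. A p-value built from them has no defined hypothesis.

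The quantity is widely used. Section 7.4.1.2 displays it for each active group and repeats the analysis for the combined 40 and 60 mg/kg group. Section 7.4.1.3 repeats it for the supportive estimand. Section 7.4.2 carries it to the secondary endpoints and puts it in the forest plots at Week 96, with a matching plot for the average over visits. Section 9 says that the MMRM results will be used to interpret the study if proportionality fails under the pMMRM. In that case percent slowing is the MMRM figure closest to the primary estimand's summary.

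**Working it through.** **Inputs** (example table at the end of SAP Section 12):
- P: mean 4.5489, SE 0.6143
- T: mean 3.0991, SE 0.5903

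The appendix prints no result, so there is no plan figure to reproduce. P-values below are 2-sided, because Section 7.4 says "However, 2-sided p-values will be reported for all tests". They use a normal reference.

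**Formulas as the appendix directs**
- Formula (1): 3.0991 / 4.5489 = 0.6813.
- Formula (2): variance = 0.5903²/4.5489² + 3.0991² × 0.6143²/4.5489⁴ = 0.01684 + 0.00846 = 0.02530, so SE = 0.1591.
- 95% CI: 0.6813 ± 1.96 × 0.1591 = 37.0% to 99.3%.

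**Definition in Section 7.4.1.2**
- Slowing: (4.5489 - 3.0991)/4.5489 = 1.4498/4.5489 = 0.3187.
- The variance of 1 - R equals the variance of R, so the SE is again 0.1591.
- 95% CI: 0.3187 ± 1.96 × 0.1591 = 0.7% to 63.0%. The 90% CI is 5.7% to 58.0%.

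**The p-value depends on a null that is not stated**

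| Null assumed | z | 2-sided p |
|---|---|---|
| Ratio = 0 (formula (1) value over its SE) | 0.6813/0.1591 = 4.28 | about 0.00002 |
| Slowing = 0, i.e. ratio = 1 | 0.3187/0.1591 = 2.00 | about 0.045 |

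As a check on the first row, set T = P = 4.5489 and keep the SEs. The ratio is 1, its SE is sqrt(0.5903² + 0.6143²)/4.5489 = 0.8519/4.5489 = 0.187, and z = 5.3. A test against 0 would be highly significant with no drug effect at all.

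**How firm 0.045 is**
- With a t reference on 50 to 300 degrees of freedom, p runs from 0.051 to 0.046.
- The covariance is not given in the documents. Assuming an LSM correlation of -0.1 to 0.2, the full variance moves the SE from 0.166 to 0.143 and p from 0.055 to 0.026.
- The plain LSM difference from the same inputs, with zero covariance, is 1.4498 with SE 0.8519: z = 1.70, p = 0.089.

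So 0.045 is one conditional value, and it differs from the LSM-difference p-value.

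**The case against.** The strongest reply is that the body of the SAP is right. Section 7.4.1.2 gives the correct formula for percent slowing and goes to the appendix only for the interval. Formula (2) gives the same SE for the ratio and for one minus the ratio, so a programmer who takes the estimate from Section 7.4.1.2 and the SE from the appendix gets 31.9% with the right width under independence. This stands, and it limits the reach of the error. It does not remove it: the appendix is the only derivation offered, and it says outright that its formulas produce the percent slowing.

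A reader might infer that the appendix tests the ratio against 0 and that p = 0.00002 is its own result. The documents do not support that. They state no null and no test statistic, and they print no outcome. Where the SAP does state a null (Section 3.3), it is no reduction in decline, which corresponds to a ratio of 1.

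A reader might also take X to be the LSM difference, to match Section 7.4.1.2. The T and P labels in the appendix table rule this out.

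On covariance, the appendix does print the full variance and makes formula (2) conditional on independence. That is fair, but its closing instruction sends the reader to formula (2). The two LSMs come from one MMRM with shared baseline CDR-SB and APOE e4 terms, so independence is not guaranteed.

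**Conclusion.** The point holds as an inconsistency between the appendix and Section 7.4.1.2. Followed literally, the appendix example reports 68.1% (95% CI 37.0% to 99.3%) where the SAP's own definition gives 31.9% (0.7% to 63.0%). Both intervals assume zero covariance and a normal reference. The p-value is undefined because no null is stated: about 0.00002 or about 0.045 under those assumptions, depending on which null is supplied. The covariance matter is secondary and cannot be sized from the documents.

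It would go too far to conclude that the trial's inference is compromised. The analysis is supportive, the primary pMMRM does not use this appendix, and the tests of LSM differences are untouched. Section 7.4.1.2 asks for an estimate and a CI for percent slowing and no p-value, and no decision rule in either document relies on one. Section 9 gives weight to the MMRM results if proportionality fails, but it does not single out a percent-slowing p-value. The correction should still be made, because the written rule is wrong.

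**What to change.** In SAP Section 12:
- Write percent slowing as 1 - X/Y, with X the treatment LSM and Y the placebo LSM, and centre the CI on that value.
- State the null as slowing = 0 (ratio = 1), or delete the reference to p-values. Deleting is simpler, since Section 7.4.1.2 asks only for a CI.
- Replace formula (2) with the full variance already printed above it, taking Cov(X,Y) from the MMRM's LSM covariance matrix.
- Say that the calculation applies at each visit and to the average over visits wherever percent slowing is reported, not only at the end-of-study visit.
- Print the example's result, so that programmers can check against it.

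The cost is a few lines of text and one extra matrix from the model output. No data collection, sample size or primary analysis changes.

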# **Statistical Analysis Plan**Protocol No. AL002-2

Last Revision Date: 12 Aug 2025

# 13. VERSION HISTORY

Version	Date	Summary of Changes	Reason for Change
1.0	31OCT2020	NA	NA
2.0	16MAY2024	SAP was rewritten.	Switch to Everest SAP template. Follow multiple protocol amendments.
		All analyses will primarily be performed for the Non-e4/e4 Set.	To align with the change in target population (see Section 5.3).
		Added the Modified iADRS endpoint and associated analyses.	The modified iADRS is a composite tool combining scores from the ADAS-Cog13 and the ADCS-MCI-ADL that provides an evaluation of clinical disease progression.
		Changed primary efficacy analysis method from Bayesian ordinal longitudinal disease progression model (DPM) to pMMRM.	DPM is deemed not well control family-wise type 1 error.
		Added sensitivity analysis using PMM.	To evaluate the impact of different patterns of missing CDR-SB values.
		Excluded those participants who received <3 doses of study drug in PPS definition.	To provide more specific requirements on dosing as part of the PPS definition.
		Added ARIA endpoints and associated analyses.	To summarize ARIA abnormalities based on MRI data.
		Added PCS criteria for safety endpoints.	To summarize safety abnormalities.
		Removed Plasma sTREM2 endpoint.	Plasma sTREM2 will not be used for decision-making due to technical interference by AL002 with the analyte.
		Added Tau PET and amyloid PET endpoints in Table 7-25.	Tau PET and amyloid PET analyses will be included in the CSR.
		Removed correlation analyses of PD biomarkers with safety, PK, immunogenicity, other PD biomarkers.	These correlation analyses are exploratory and excluded from the CSR.
